1. STUDY OBJECTIVES

1.1. Primary Objective

The primary objective is to assess the effect of voxelotor compared to placebo on improvement in hemoglobin.

1.2. Secondary Objectives

The secondary objectives are to evaluate the effects of voxelotor compared to placebo on:

- clinical measures of hemolysis
- long term VOC incidence

1.3. Exploratory Objectives

The exploratory objectives are to evaluate the effects of voxelotor compared to placebo on:

- Sickle Cell Disease Severity Measure (SCDSM)
- EuroQol EQ-5D-5L health questionnaire (EQ-5D-5L™)
- Clinical Global Impression of Change (CGIC)- Groups 1 and 2 only
- Incidence and time to first RBC transfusion and post baseline onset of VOC
- School and/or work attendance and the use of opioid during the treatment period as recorded via eDiary
- Measures related to SCD pathophysiology and their utility as pharmacodynamic markers to evaluate including inflammatory biomarkers (Part 1 only), kidney function and RBC rheology
- Measures predictive of response to voxelotor

1.4. Safety Objectives

The safety objectives are to assess the safety of voxelotor compared to placebo based on AEs, clinical laboratory tests, physical examinations, and other clinical measures (eg, discontinuations due to AEs, dose reductions).

1.5. Pharmacokinetic Objective

The PK objective is to assess the PK of voxelotor as evaluated by population PK analysis.

2. INVESTIGATIONAL PLAN

2.1. Study Design

This study is a randomized, placebo-controlled, double blind, parallel group, multicenter study of participants, age 12 to 65 years (refer to [Section 2.1.1](#)), with SCD (HbSS, HbSC, HbS β thalassemia, or other sickle cell syndrome variants). The study is composed of 3 groups as described below and in [Figure 1](#).

Study procedures and assessments are outlined in [Section 4](#). Dosage and treatment administration are outlined in [Section 5](#). The Study Schematic is provided in [Figure 1](#)

The key purposes for each of the 3 study groups are:

Group 1:

- Evaluate safety and efficacy of voxelotor (900mg and 1500mg) compared to placebo.
- Selection of voxelotor dose(s) for further study in Group 3.

Group 2:

- Enable a seamless transition from Group 1 to Group 3 by continuing enrollment and data collection until completion of Group 1 analysis.
- If needed, data from Group 2 may be included in the Group 1 analysis to inform dose selection and potential study modification as appropriate.
- Form the basis for the primary analysis of the study to establish the efficacy and safety of voxelotor, in combination with Group 1.

Group 3: Further investigate the effect of voxelotor at selected dose(s), eg, in participant subgroups as determined from the primary analysis of the study based on data from Group 1 and Group 2 combined.

2.1.1. Adolescent Participants

Initially only adult participants will be enrolled. Adolescent participants (12 to <18 years) will be included in enrollment/randomization when:

1. Single dose PK data and modeling from a previous study are available to confirm the appropriate dose for adolescent participants, and
2. The DSMB has reviewed the safety data from at least 18 adults randomized in this study of which at least 6 adults have received 1500 mg voxelotor for at least 4 weeks to confirm acceptable safety and tolerability before adolescents can be enrolled. Sites will be notified when adolescent participants can be enrolled in this study.

At the time that these criteria are met, adolescents will begin to enroll (as early as Group 1); a minimum of 50 adolescents will be included in this study.

2.1.2. Study Conduct: Group 1

Approximately 60 participants will be randomized in Group 1 in a 1:1:1 ratio to receive voxelotor 900 mg, voxelotor 1500 mg, or matching placebo.

The randomization procedure and participant enrollment are discussed in [Sections 5.3 and 6](#), respectively. Guidelines for enrollment of adolescents are outlined in [Section 6.1.1](#). Details regarding study blinding are provided in [Section 6.2](#).

When the 60th participant reaches 12 weeks of treatment, data from the 60 participants will be unblinded, and an analysis of Group 1 will be conducted to inform the dose selection and other potential protocol modifications for Group 3 study conduct. The voxelotor dose(s) for Group 3 will be determined from the unblinded analysis of efficacy and safety endpoints, and PK/PD.

2.1.3. Study Conduct: Group 2

Approximately 180 participants will be randomized in Group 2 in a 1:1:1 ratio to receive voxelotor 900 mg, voxelotor 1500 mg, or matching placebo. Group 2 enrollment will begin with participant #61 and will end when the Group 3 dose(s) has been selected.

2.1.4. Study Conduct: Group 3

Group 3 sample size (currently planned for approximately 65 participants per dose arm) will be evaluated when the voxelotor dose(s) is selected. Additional considerations (eg, selection of a dose other than those studied in Groups 1 and 2) may also be generated on the basis of findings from the analysis of Groups 1 and 2.

2.1.5. Open Label Extension Study (Under a Separate Protocol-)

Following completion of study treatment, eligible participants will be given the option to enroll in an open label extension study to receive voxelotor at the selected dose(s)

The open label extension study will be available to eligible participants who:

- Were included in the Group 1 Analysis regardless of the treatment arm to which they were randomized.
- Were randomized in Group 2 to the voxelotor dose not selected for Group 3.
- Were randomized in Group 2 and unblinded for data analysis combined with Group 1 data.
- Were included in Group 3 and Group 2 participants randomized to placebo or the selected dose(s) and completed through end of treatment.

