
Duration of Study Participation
	
Duration of Treatment
 
Group 1: Minimum duration is 12 weeks, maximum duration is 72 weeks.
 
Group 2: Minimum duration is 2 weeks, maximum duration is 72 weeks.
 
Group 3: Minimum duration is 24 weeks, maximum duration is 72 weeks.
 
Duration of Study
 
The study will end when the Group 3 last participant last visit occurs which will be approximately 28 weeks after randomization for the last participant enrolled into Group 3.
 
Duration of study for an individual participant includes Screening (at least 28 days, but up to 35 days to account for Screening window flexibility), treatment for a minimum of 2 weeks and a maximum of 72 weeks, and an End of Study (EOS) visit at 4 weeks (\pm 7 days) after the last dose of study drug. From Screening through follow-up, total participation in this study for an individual participant may last from approximately 10 weeks to up to 81 weeks. The minimum study duration is approximately 10 weeks (for participants in Group 2 enrolled at a dose not selected for Group 3). Participants will continue to be followed for efficacy and safety through at least the endpoint visit (Week 12 for Group 1 and Week 24 for the Main Population) regardless of treatment discontinuation.

Study Population
	
INCLUSION CRITERIA
 
1. Male or female study participants with sickle cell disease

- Documentation of SCD genotype (HbSS, HbSC, HbS β thalassemia or other sickle cell syndrome variants) may be based on history of laboratory testing or must be confirmed by laboratory testing during screening
2. Participants have had at least 1 episode of VOC in the past 12 months. For study eligibility, VOC is defined as a previously documented episode of ACS or acute painful crisis (for which there was no explanation other than VOC) which required prescription or healthcare professional-instructed use of analgesics for moderate to severe pain (documentation must exist in the patient medical record prior to Screening)
 3. Age 12 to 65 years
 4. Hemoglobin (Hb) ≥ 5.5 and ≤ 10.5 g/dL during Screening
 5. For participants taking HU, the dose of HU (mg/kg) must be stable for at least 3 months prior to signing the ICF and with no anticipated need for dose adjustments during the study, in the opinion of the Investigator

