2.1.6. Duration of Study

The study will end when the last participant's last visit occurs which is approximately 72 weeks after randomization of the last participant.

Duration of study for an individual participant includes Screening (at least 28 days, but up to 35 days to account for window flexibility), treatment for a minimum of 2 weeks and a maximum of 72 weeks, and an End of Study (EOS) visit at 4 weeks (\pm 7 days) after the last dose of study drug. From Screening through follow-up, total participation in this study for an individual participant may last from approximately 10 weeks to up to 81 weeks. Participants will continue to be followed for efficacy through at least the primary efficacy period regardless of treatment discontinuation.

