2.1.7. Duration of Treatment

The duration of treatment for each of the 3 study groups is as follows:

Group 1:

Minimum duration is 12 weeks, maximum duration is 72 weeks.

Group 2:

Minimum duration is 2 weeks, maximum is duration 72 weeks.

Group 3:

Minimum duration is 24 weeks, maximum duration is 72 weeks.

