6.2.1.1. Unblinding for Group 1 Analysis

To facilitate the Group 1 analyses, certain Sponsor representatives and Sponsor designees will be unblinded to treatment assignments prior to and during the data analysis (including the biostatistics contract research organization [CRO], Sponsor Biostatistics and Programming staff, and external groups for bioanalytical PK/PD). However, the rest of the Sponsor study team, including all study team members who have direct interactions with study sites, was not unblinded to individual treatment assignment. No site staff or study participants will be unblinded to randomization assignment.

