- b Visits at Week 2 and Week 6 may be removed for patients enrolled into Groups 2 and 3, pending data analysis from Group 1.
- c Participants will complete a minimum of 24 weeks and a maximum of 72 weeks of treatment with study drug. Screening for participants will end when approximately 300 participants have been randomized.
- d Physical examination (PE) will be a complete PE at Screening, Week 24, Week 48, Week 72, and at the Follow-up Visit; and may be abbreviated PE at all other visits.
- e Adult participants (those who are 18 years of age and older) will only have height measured at Screening. Participants 12 to <18 will have height measured at Weeks 24, 48, 72, and EOS.
- f Vital signs (blood pressure [BP] and pulse rate) will be measured after a participant has rested for at least 5 minutes in the supine or recumbent position. A repeated measurement of HR and BP will be taken within 5 minutes if the first reading is outside the normal range and deemed clinically significant.
- g Electrocardiograms (ECG) (12-lead) will be recorded after a participant has rested for at least 5 minutes in the supine position.
- h The EQ-5D-5L™ questionnaire will be implemented in each country when available (pending translation and cultural validation requirements).
- i Hematology assessments will be performed through a central laboratory and will include: Red blood cell (RBC), hematocrit (Hct), hemoglobin (Hb), platelets, white blood cell (WBC) (with differential: basophils, eosinophils, neutrophils, monocytes, and lymphocytes), % reticulocytes, absolute reticulocytes, % dense cells (% hyperchromic RBCs), RBC distribution width (RDW), Hb distribution width (HDW), cell hemoglobin concentration mean (CHCM), mean corpuscular volume (MCV) and mean corpuscular hemoglobin concentration (MCHC).
- j Exploratory assessments related to measures relevant to SCD pathophysiology and to evaluate measures predictive of response to voxelotor will be performed through a central laboratory and may include but not limited to: serum cystatin C, urine albumin to creatinine ratio, carboxyhemoglobin, VCAM, ICAM, soluble P-selectin and E-selectin (and other exploratory measures that may be related to disease activity) will be completed for Group 1 only.

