2.1. Study Overview

This study is a randomized, placebo-controlled, double blind, parallel group, multicenter Phase III study, evaluating the safety and efficacy of voxelotor at 1500 mg and 900 mg dose level. Subjects meeting enrollment criteria were randomized in a 1:1:1 ratio to receive a daily dose of voxelotor 1500 mg, voxelotor 900 mg or placebo. The treatment duration was at minimum 12 weeks and may continue to a maximum of 72 weeks, with a key study endpoint of 24 weeks for the primary analysis of efficacy. The study will continue until all randomized subjects have reached Week 72 or discontinue from study early.

The study population includes SCD subjects with HbSS, HbSC, HbS β thalassemia, or other sickle cell syndrome variants. Subjects with 2 sickle hemoglobin genes (HbSS) or with compound heterozygosity for sickle Hb gene and beta thalassemia with no β globin expression (β 0 thal) thalassemia (HbS β 0 thal) are the SCD genotypes with most severe hemolysis and clinical symptoms. A history of at least one VOC in the past 12 months is required for enrollment. Subjects are also required to have Hb levels \leq 10.5 g/dL and \geq 5.5 g/dL.

SCD symptoms extend from infancy to adulthood. The population of this study includes adult and adolescent subjects (12 to 65 years).

Adolescent Subjects:

The study was to enroll only adult subjects initially. Adolescent subjects (ages 12 to <18 years) would be included in enrollment/randomization when:

1. Single dose PK data and modeling from Study GBT440-007 (pediatric subjects, 12-17 years of age) were available to confirm the appropriate dose for adolescent subjects, and
2. The DSMB had reviewed the safety data from at least 18 adults enrolled in this study of which at least 6 adults have received 1500 mg voxelotor for at least 4 weeks to confirm acceptable safety and tolerability before adolescents can be enrolled.

At the time that these criteria were met, adolescents would begin to enroll (as early as Group 1); a minimum of 50 adolescents would be included in the primary analysis of the study.

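### Extension-entry and minimum-duration rules left from a dose-dropping design would give the non-selected dose in Group 2b shorter follow-up after Week 24 than placebo, and the stated minimums contradict each other

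*Protocol*

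**What the plan says.** **Extension entry.** Protocol 2.1.5 and the synopsis list four routes. Two do not depend on arm: inclusion in the Group 1 analysis, and membership of the part of Group 2 unblinded with Group 1 (called Group 2a in the SAP). The other two do. One covers those who "Were randomized in Group 2 to the voxelotor dose not selected for Group 3". The other covers those who "Were included in Group 3 and Group 2 participants randomized to placebo or the selected dose(s) and completed through end of treatment". Only the last carries a completion condition of its own.

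**Minimum duration.** The synopsis ties the shortest participation to one arm: "The minimum study duration is approximately 10 weeks (for participants in Group 2 enrolled at a dose not selected for Group 3"). For treatment, Protocol 2.1.7 says of Group 2: "Minimum duration is 2 weeks, maximum is duration 72 weeks". It gives Group 1 a 12-week minimum. Appendix A footnote c says: "Participants will complete a minimum of 24 weeks and a maximum of 72 weeks of treatment with study drug". SAP 2.1 says: "The treatment duration was at minimum 12 weeks and may continue to a maximum of 72 weeks".

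**Follow-up after stopping.** Protocol 2.1.6: "Participants will continue to be followed for efficacy through at least the primary efficacy period regardless of treatment discontinuation". Section 4.14.2.2 sets the endpoint visit at Week 12 for Group 1 and Week 24 for Groups 2 and 3. The synopsis gives Week 12 for Group 1 and Week 24 for the Main Population, which its extension list describes as Group 3 plus Group 2 placebo and selected dose.

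**Analysis.** Protocol 8.2.2 and SAP 6.1 base the primary analysis on all 274 participants in Groups 1 and 2. The 900 mg arm holds hypotheses 5 to 9 of the test sequence. SAP 8.2.2.2 models VOC counts to Week 72 by negative binomial regression, states no follow-up offset, and does not mention extension entry. SAP section 4 censors time to first VOC at end of study.

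**Blinding.** Protocol 6.2.1.1: "No site staff or study participants will be unblinded to randomization assignment". Protocol 6.2 keeps sites and participants blinded generally, and SAP 6.2 repeats this for the Group 1 and 2a analyses.

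**The concern.** The exit rules belong to a design in which the non-selected dose is dropped and its participants are no longer needed. The present design needs them: that arm is compared with placebo at Week 24 and again for VOC to Week 72. If one arm may leave while its comparator must finish, the two are observed for different lengths of time. A model of event counts with no allowance for time would then show fewer crises in the arm watched for less time. An extension offered because of the randomized dose also tells the site which dose it was.

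Separately, the documents give sites three minimum treatment durations, and they give Group 1 a protected visit (Week 12) that comes before the Week 20 and Week 24 hemoglobin values on which the primary endpoint rests.

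**Working it through.** **1. The protocol's own participation range.** Screening plus treatment plus a 4-week end-of-study visit:
- minimum 4 + 2 + 4 = 10 weeks; maximum 5 + 72 + 4 = 81 weeks. Both stated figures reproduce.
- a 12-week treatment minimum would give 20 to 21 weeks, and a 24-week minimum 32 to 33.

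So the 10-week figure needs the 2-week minimum and conflicts with footnote c and SAP 2.1. It also puts the end-of-study visit 2 + 4 = 6 weeks after randomization, which conflicts with following Group 2 to Week 24 regardless of treatment discontinuation.

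**2. Who is under an arm-dependent rule.** From the SAP Introduction: Group 1 = 62, Group 2a = 94, Group 2b = 118, all randomized 1:1:1.
- Groups 1 and 2a: 62 + 94 = 156, or 52 per arm, with the same entry rule in every arm.
- Group 2b: 118/3 = about 39 per arm. Only here does the rule differ by arm.
- Affected: about 39 of 274/3 = about 91 on the non-selected dose; 39.3/274 = 14% of the trial.
- Group 1, with the Week 12 protected visit: 62/274 = 23%.

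**3. Person-years to Week 72.** Neither document gives an exit week, so these are assumptions. With everyone else staying to Week 72:

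(52 × 72 + 39.33 × exit week) / 52.18, against (52 × 72 + 39.33 × 72) / 52.18 = 126.0 for placebo.

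| Assumed exit week, Group 2b non-selected dose | Person-years | Ratio to placebo |
|---|---|---|
| 2 | 73.3 | 0.58 |
| 24 | 89.8 | 0.71 |
| 48 | 107.9 | 0.86 |
| 72 | 126.0 | 1.00 |

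If Groups 1 and 2a also left at Week 24 in every arm, the Week 24 row would become 42.0 against 78.2, a ratio of 0.54. If only Groups 1 and 2a left early, the ratio would stay at 1.00.

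**4. Effect on the VOC model, read literally.** Simulation of 300 trials per setting: no true effect, 91 per arm, assumed 1.5 or 3.0 crises per year, assumed dispersion 0.8, treatment as the only term, Groups 1 and 2a staying to Week 72.
- Group 2b exit at Week 24, no offset: mean rate ratio 0.71, rejection at 0.05 in 47% to 56% of trials.
- Exit at Week 2, no offset: 0.59, rejection in 73% to 78%.
- Same data with a log follow-up offset: 0.99 to 1.02, rejection in 6% to 8%.
- Equal follow-up, for reference: 0.98 to 0.99, rejection in about 6%.

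**The case against.** The case on the other side is substantial, and most of it stands as a limit on scope.

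- **Completion.** Section 2.1.5 opens by placing extension entry after completion of study treatment, ahead of all four routes. But completion is not defined there, one route repeats the condition while the others do not, and the synopsis ties the 10-week minimum to the non-selected dose. The text is ambiguous; it does not settle the matter.
- **Trigger.** The rule bites only if a dose is not selected. No one had entered Group 3, neither document names a dropped dose, and Protocol section 6 allows Group 3 three arms. This stands: the effect is conditional.
- **Continued assessment.** Section 4.14.2.1 keeps most participants who stop treatment in study assessments, and SAP 2.1 runs the study until all reach Week 72 or discontinue early. Neither says whether extension entry counts as leaving.
- **Standing of VOC.** It is secondary and outside the test sequence, and an annualized rate and mean cumulative function are planned. An analyst may well include an offset, but the SAP does not state one.

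A reader might infer more than the documents support:
- Adding Groups 1 and 2a to the affected Group 2b participants gives 156/274 = 57%, or (156 + 39)/274 = 71%. These do not measure imbalance, because the Group 1 and 2a rules are the same in every arm.
- Exit set by randomized arm makes follow-up unequal. It is not shown to depend on outcome, so informative censoring is not established.
- Early leavers need not become non-responders in hypothesis 5. Section 4.14.2.2 takes Group 2 to Week 24, and SAP 6.3.5.1 accepts one of the Week 20 and Week 24 values.
- An extension offer in Group 1 or 2a says nothing about arm.

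**Conclusion.** The concern holds within narrow limits. Followed as written, and only if a dose is not selected, the extension rule gives about 39 Group 2b participants (14% of 274) an earlier exit than their placebo counterparts. VOC and hemoglobin follow-up after Week 24 would then be unequal for the non-selected dose versus placebo: a person-year ratio of 0.58 to 0.86 for assumed exits between Weeks 2 and 48 with all others staying. An early offer in Group 2b would identify the arm, contrary to the blinding statements. Selected dose versus placebo is under one rule in every cohort and is unaffected.

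The Week 24 hemoglobin analysis is largely protected for Group 2, provided section 4.14.2.2 governs rather than the synopsis wording. For Group 1, follow-up after stopping is protected only to Week 12, although the primary endpoint uses Weeks 20 and 24.

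The contradiction between minimums of 2, 12 and 24 weeks needs no assumption. The simulated error rates do: they rest on assumed exit weeks, crisis rates and dispersion, and on fitting the VOC model without an offset. They show direction and rough size only.

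**What to change.** **Protocol.** Reconcile the synopsis (extension and duration text), 2.1.5, 2.1.6, 2.1.7, 4.14.2.2, Appendix A footnote c and SAP 2.1 with one another, with the all-arms primary analysis and with the blinding statements. Define completion of study treatment where extension entry refers to it. The sponsor decides the rule and the week; none is proposed here. Align Group 1's protected follow-up visit with the Week 24 primary endpoint.

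**SAP.** In 8.2.2.2, state log follow-up time as the offset in the negative binomial VOC model. Record extension entry as its own censoring reason in the VOC analyses, including time to first VOC. Add a sensitivity analysis of VOC with follow-up truncated at one pre-stated time common to all arms.

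**Cost.** A protocol clarification or amendment and a few SAP lines, settled before Group 2b is unblinded. No added participants. The truncated analysis discards some late follow-up, so it is a sensitivity analysis only. The offset corrects for length of follow-up; it would not correct for exit related to outcome, which is why extension entry should be recorded separately.

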2.1.6. Duration of Study

The study will end when the last participant's last visit occurs which is approximately 72 weeks after randomization of the last participant.

Duration of study for an individual participant includes Screening (at least 28 days, but up to 35 days to account for window flexibility), treatment for a minimum of 2 weeks and a maximum of 72 weeks, and an End of Study (EOS) visit at 4 weeks (\pm 7 days) after the last dose of study drug. From Screening through follow-up, total participation in this study for an individual participant may last from approximately 10 weeks to up to 81 weeks. Participants will continue to be followed for efficacy through at least the primary efficacy period regardless of treatment discontinuation.

